1. Develop an algorithm for using the method of transfusion of hematopoietic umbilical cord blood cells in the treatment of patients with autistic type disorder.
2. To formulate criteria for the selection of patients for this technique.

3. To analyze the efficacy and safety of transfusion of hematopoietic cord blood cells in patients with autistic type disorder using rating scales.
4. Introduce the method of transfusion of cord blood hematopoietic cells to patients with autistic type disorder in the complex therapy of patients with autistic type disorder.

OBJECT OF STUDY

The protocol for testing the method will be carried out on 10 patients with autism spectrum disorder by transfusion of hematopoietic cord blood cells. As a control group, 10 patients with a similar pathology will be examined, comparable in age, gender and degree of autistic disorder according to the “paracopy” type against the background of standard therapy.

Type of study: interventional, prospective, non-randomized with a control group.

Patient selection criteria (indications for this type of treatment):

- age of the patient is from 3 to 15 years.
- Diagnosis: autistic disorder.
- Systemic speech underdevelopment
- The presence of attention deficit hyperactivity disorder as a comorbid state
- Cognitive impairment

Patient exclusion criteria (contraindications for this type of treatment):

- The patient's under 3 years, after 15 years;
- The presence of organic pathology of the brain according to CT, MRI
- The presence of the following diseases in the anamnesis: heart failure in the stage of decompensation, a history of stroke less than 1 year ago, anemia and other blood diseases;
- Decompensation of chronic and endocrinological diseases;
- Acute respiratory viral and bacterial infections, period less than 1 month after the acute phase.
- HIV infection, hepatitis B and C.
- Cancer, chemotherapy and history of cancer;
- Tuberculosis.
- Severe form of intellectual disability as a concomitant disease (diagnosis can be ignored, according to the decision of the Medical Committee of the Center);
- Cerebral palsy.
- Increased convulsive readiness, epilepsy.

Indications and contraindications to this type of treatment for each patient are determined at a consultation of doctors with the participation of a paediatrician or a psychologist (psychiatrist), and transfusiologist.

Research methods

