Evaluation scales CARS, ATEC (to assess the dynamics). Neuropsychological examination, examination of a speech therapist-pathologist. Assessment of neurological status. Determination of the immune status by flow cytometry (CD3; CD4; CD8; CD19; CD16-56). Determination of the level of cytokines in peripheral blood: interleukin 1 beta, interleukin 6, tumor necrosis factor alpha, interleukin 8, gamma interferon. Determination of the HLA genotype of the subject parents and siblings.

The results will be statistically processed using parametric and non-parametric statistics methods using STATA version 9.0, Statistica for Windows version 6.0 and MS Office Excel 2007. Changes from the start of therapy and after 1, 2, 6, 12 months will be compared using the Wilcoxon criterion, comparing data between the main group and the control group using non-parametric method, using the Mann-Whitney test (data are presented in Me - median format with an indication of 25% (q1) and 75% (q3) quartile.

Treatment protocol

Selection of patients and assessment of their psychological status, transfusion of umbilical cord blood HSC in the conditions of day hospital is carried out by specialists of the State budgetary institution of public health "Samara Regional Children's Clinical Hospital N.N. Ivanova Laboratory examination, selection of biomaterial will be carried out by the State Budgetary Institution "MC Dynasty".

Stage 1 - selection and examination of the patient, determination of indications and contraindications to this method of treatment is carried out by a child neurologist, pediatrician (pediatrician), medical psychologist. Assessment of autism disorder is carried out according to the assessment scales of CARS, ATEC.

A prerequisite for inclusion:

- diagnosed with autism spectrum disorder by a psychiatrist,
- Dispensary supervision by a child psychiatrist at the place of residence.

Mandatory general clinical trials (clinical and diagnostic laboratory):

- a) General clinical blood tests (erythrocytes, hemoglobin, platelets, clotting time, leukocytes + formula, COE) - shelf-life 14 days.
- b) general clinical urine test - shelf life 14 days.
- c) feces per helminth eggs - shelf life 14 days.
- d) blood type and rhesus factor.

A patient who meets the selection criteria and has no contraindications for this type of treatment enters into a protocol and signs an informed consent (or his/her legal representative).

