Stage 2 - umbilical cord blood sampling. It is performed by a transfusion doctor of the State Budgetary Institution "MC Dynasty".

The selection criteria for the sample will be the following parameters:

1. Blood group compatibility by system AB0 and Rh
2. Infectious safety (negative HIV test results, hepatitis B and C, syphilis, herpes simplex virus, cytomegalovirus, toxoplasmosis)
3. No bacterial or fungal contamination.
4. Number of hematopoietic cells (mononuclears) in the range of 20-50 million cells per kg of patient weight.

Stage 3 - intravenous injection of hematopoietic cells in umbilical cord blood.

Preliminary examination of the patient and relatives:

- a) Determination of immune status by flow cytometry (SD3; SD4; SD8; SD19; SD16-56) - patient.
- b) Determination of cytokine levels in peripheral blood: interleukin 1 beta, interleukin 6, tumor necrosis factor alpha, interleukin 8, gamma-interferon - patient.
- c) Determination of HLA genotype by loci A, B, DRB1 - patient and parent, sibling.

The sample consists of a suspension of hematopoietic cells diluted in 10 ml 0.9% NaCl + 10 ml 6% hydroxyethyl starch in a disposable syringe labeled by the manufacturer (label).

The patient is injected in drops with the use of infusion. The rate of administration is 60 - 70 ml per hour. Immediately at the beginning of injection, a biological compatibility test should be performed.

Three-fold injection is planned at an interval of 1 month.

Possible area of application

Specialized hospitals.

Data to be obtained during implementation

- correct selection of criteria for selecting patients for treatment of patients with autism type disorder;
- developed algorithm for using the method of transfusion of hematopoietic cells of umbilical cord blood in complex therapy of patients with autism type disorders;
- information on the efficacy and safety of treatment of patients with autism-type disorder by transfusion of hematopoietic cells of umbilical cord blood;
- appropriateness and effectiveness of this method of treatment. To evaluate its impact on treatment tactics and results;
- Association of HLA genes with the development of autism spectrum disorders;
- relationship between immune status and cytokine profile and severity of the disease.

Therapy evaluation criteria

Evaluation of the effect of treatment is carried out 1, 2, 3 and 6 months after treatment.

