The results will be statistically processed using parametric and non-parametric statistics methods using STATA version 9.0, Statistica for Windows version 6.0 and MS Office Excel 2007. Changes from the start of therapy and after 1, 2, 6, 12 months will be compared using the Wilcoxon criterion, comparing data between the main group and the control group using non-parametric method, using the Mann-Whitney test (data are presented in Me - median format with an indication of 25% (q1) and 75% (q3) quartile.

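### The plan promises an association of HLA genes with developing ASD, but every enrolled child has ASD, the named tests cannot estimate it, and no family-based analysis of the typed relatives is specified

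*Combined protocol and SAP*

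**What the plan says.** The list under *Data to be obtained during implementation* includes "Association of HLA genes with the development of autism spectrum disorders".

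On who is enrolled, *Object of study* says "The protocol for testing the method will be carried out on 10 patients with autism spectrum disorder", and continues "As a control group, 10 patients with a similar pathology will be examined, comparable in age, gender and degree of autistic disorder". The prerequisites for inclusion under Stage 1 of the treatment protocol require that the child be "diagnosed with autism spectrum disorder by a psychiatrist".

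On who is typed, *Research methods* has "Determination of the HLA genotype of the subject parents and siblings". Stage 3 of the treatment protocol, the injection stage, has "Determination of HLA genotype by loci A, B, DRB1 - patient and parent, sibling".

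On analysis, the same paragraph appears under *Research methods* and at the end of *Statistical considerations*. It refers generally to parametric and non-parametric methods, then names the Wilcoxon test for change from the start of therapy and, between groups, "comparing data between the main group and the control group using non-parametric method, using the Mann-Whitney test". Results are to be shown as medians and quartiles. No analysis of HLA data is described anywhere.

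**The concern.** An association with developing a disorder can be estimated in two ways: disease status varies among the people compared, or alleles are compared within families (transmitted against non-transmitted parental alleles, or affected against unaffected siblings). Disease status does not vary among the enrolled children, because the control group is also affected and is chosen to be comparable in degree of disorder. The two named tests suit scale scores and laboratory values followed over time. HLA genotype is categorical and fixed, so there is no change for Wilcoxon to test. Mann-Whitney between the two groups would at most compare two sets of affected children.

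The deliverable therefore has no comparator, hypothesis, test or multiplicity rule. Three loci with many alleles each, examined in a few families with nothing prespecified, leave room for a chance pattern to be read as a genetic link with ASD.

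**Working it through.** The plan gives no alpha, power, effect size or sample-size basis for the HLA item, so there is no figure to reproduce. The check has two parts.

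**1. What the named tests can estimate**

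- Treated children: 10, all with ASD. Control children: 10, all with a similar pathology. Unaffected enrolled children: 0 of 20.
- Since disease status is constant across the 20, an HLA difference between groups would reflect chance or the non-randomised allocation. It could not reflect a link with developing ASD.
- The typed relatives are the only possible comparator in the plan. Three things needed to use them are unsettled:
  - *Which relatives.* Stage 3 has parent and sibling in the singular; *Research methods* has both in the plural.
  - *Which families.* The detailed typing item, with its loci, sits under the injection stage, so it may cover 10 families or 20.
  - *Sibling phenotype.* Recording siblings' ASD status is not mentioned, and a sibling comparison needs it.

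**2. What a family-based test could achieve at this size**

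The most favourable standard case is a transmission test in complete trios.

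From the plan: 10 families (treated only) or 20 (both groups).

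Assumed, not in the documents: both parents typed; Hardy-Weinberg proportions; two-sided alpha 0.05 for one allele; allele frequency p from 0.1 to 0.5; over-transmission of 2:1 or 3:1, so the transmission probability t is 2/3 or 3/4.

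Formulas:

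- Probability that a parent is heterozygous, hence informative: h = 2p(1 − p). At p = 0.2, h = 2 × 0.2 × 0.8 = 0.32.
- Expected informative parents: 2 × trios × h. For 10 trios at p = 0.2, 20 × 0.32 = 6.4.
- Exact two-sided binomial test of t = 0.5. With 5 informative parents the smallest attainable p-value is 2 × 0.5^5 = 0.0625, so significance is impossible. With 6, all must transmit the same allele: 2 × 0.5^6 = 0.031.
- Power with exactly 6 informative parents: (2/3)^6 + (1/3)^6 = 0.089 for 2:1, and 0.75^6 + 0.25^6 = 0.178 for 3:1.
- The number of informative parents is itself random, Binomial(2 × trios, h), so power is averaged over that distribution. For 10 trios at p = 0.2 the average is 0.052 (2:1) and 0.114 (3:1). This is lower than at exactly 6, partly because draws of 5 or fewer contribute nothing.

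Averaged power:

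| Complete trios | Allele frequency | Expected informative parents | 2:1 | 3:1 |
|---|---|---|---|---|
| 10 | 0.1 | 3.6 | 1% | 2% |
| 10 | 0.2 | 6.4 | 5% | 11% |
| 10 | 0.5 | 10.0 | 11% | 24% |
| 20 | 0.1 | 7.2 | 6% | 14% |
| 20 | 0.2 | 12.8 | 15% | 33% |
| 20 | 0.5 | 20.0 | 25% | 55% |

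Dividing alpha only by the three loci (0.05/3 = 0.0167) reduces the 20-trio figures at p = 0.2 to 6% and 18%. Correcting for the alleles within each locus would reduce them further.

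For scale, 80% power at 2:1 and alpha 0.05 needs about 77 informative parents. That is about 77 trios at p = 0.5 (77 / (2 × 0.5)) and about 121 at p = 0.2 (77 / (2 × 0.32)).

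**The case against.** The strongest reply is that the plan types parents and siblings, and family-based association needs only affected children and their relatives. This stands. A reader might infer from the all-affected enrolment that the design rules the result out. The documents do not support that: an estimate is possible in principle, and the general reference to parametric and non-parametric methods does not exclude a family-based test. What is missing is the specification, and the number of families is small.

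Two further inferences also go too far. One is that only one parent is typed, so that a transmission test is impossible. The singular in Stage 3 conflicts with the plural in *Research methods*, in what reads as a translated text; that is an ambiguity to resolve, not proof of the narrower reading. Nor is a trio test the only option, since siblings are typed as well. The other is that the sponsor means to compare HLA between treated and control children. Nothing says so: the Mann-Whitney sentence follows the one on change over time and fits scores and laboratory values. The point is only that, if the named tests were applied to HLA, they would not answer the question.

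It is also fair to say that the item is one bullet of six, absent from the clinical purpose and from the four tasks. That lowers its weight but does not remove the gap.

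**Conclusion.** The point holds in limited form. Following the plan as written gives no valid basis for a conclusion on HLA and the development of ASD. The planned family typing could supply one, but no family-based test, sibling phenotype, multiplicity rule or size basis is given, and the wording on who is typed is not consistent.

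Under the favourable assumption of complete trios, power for a single allele stays between about 1% and 24% with 10 families and between about 6% and 55% with 20, across the assumed range of allele frequency (0.1 to 0.5) and over-transmission (2:1 or 3:1), before correction for multiple alleles. The upper ends need a very common allele and a strong effect. These figures rest on assumed inputs, but the absence of a specified analysis does not depend on them.

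Severity is minor: the item is secondary, and the efficacy and safety analyses are unaffected.

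**What to change.** Preferred: replace the bullet under *Data to be obtained during implementation* with a description of HLA-A, -B and -DRB1 types in the enrolled children and relatives, labelled hypothesis-generating, with no conclusion to be drawn on the development of ASD.

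If a test is kept, state in *Statistical considerations*:

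- that it is exploratory and family-based: a transmission test in complete trios, or a sibling-based test with siblings' ASD status recorded;
- the correction for the number of alleles tested;
- that HLA in treated against control children will not be used as evidence on the development of ASD.

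Under either option, make *Research methods* and Stage 3 agree on who is typed (one or both parents, which siblings), and say whether control families are included.

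Cost: wording only for the descriptive version, at the price of a less ambitious deliverable. Keeping a test adds the recording of sibling status if the sibling route is chosen, and may add typing of second parents or control families if these are not already intended.

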To assess the therapeutic efficacy of using core blood cells, during the research studies the CARS, CGI and ABC scales were used. CARS provides descriptive information about pathological behaviour and classifies severity in children with autism, while the CGI scale, as a global measure, indicates a noticeable overall treatment effect. However, further research will need to extend the rating scales to standardize the diagnosis and treatment of autism in detail.

In 2011, a Chinese research group from the Shenzhen Beike Bio-Technology Co. conducted a scientific clinical research study of the use of intravenous mononuclear cord blood cells in patients diagnosed with autism. In total, 37 patients aged 3 to 12 years were tested. There were 3 clinical groups: Group 1 consisted of 14 patients receiving the injections of mononuclear cord blood cells

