Evaluation of the effect is carried out using the scales used in the introduction to the protocol, evaluation of the neurological and psychological status of the patient.

Evaluation of immune status indicators is carried out 6 months after the last injection.

Cytokine profile is assessed 1, 2, 3 months after the first injection.

Expected results:

It is assumed that transfusions of hematopoietic cord blood cells in patients with autism spectrum disorders will not cause adverse reactions and complications (safe) and will lead to improved social interaction and communication of patients, increased social adaptation, reduced stereotyping, increased self-service skills, increased cognitive functions.

STATISTICAL CONSIDERATIONS

This study will enroll autistic children age 3 to 15 years of age.

Participants will be carried out on 10 patients with autism spectrum disorder by transfusion of hematopoietic cord blood cells. As a control group, 10 patients with a similar pathology will be examined, comparable in age, gender and degree of autistic disorder according to the “paracopy” type against the background of standard therapy.

This is interventional, prospective, non-randomized with a control group study with three intravenous allogeneic, unrelated CB infusion in children ages 3-15 years with ASD/

The primary outcomes will be assessed 1, 2,3,6 and 12 months after the initial infusion in the sequence. Duration of study participation will be 12 months from the time of baseline infusion.

Accrual

It is estimated that up to 2-3 research participants will be enrolled each week and that approximately 4 weeks of accrual will be necessary to enroll 10 participants.

Study Duration

Research participants will be followed for safety for 12 months after the third study infusion.

Demographics and Baseline Characteristics

Demographics and baseline characteristics will be summarized for all research participants. Characteristics to be examined include age, sex, and baseline behavioral status (ATEK).

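### The primary outcomes are not named and have no decisive visit, significance level or multiplicity rule, and the three visit lists conflict, so any scale and visit could carry the efficacy conclusion

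*Combined protocol and SAP*

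**What the plan says.** STATISTICAL CONSIDERATIONS speaks of primary outcomes in the plural and gives five times: "The primary outcomes will be assessed 1, 2,3,6 and 12 months after the initial infusion in the sequence". No scale is attached to them there or elsewhere. Research methods names two scales without ranking them: "Evaluation scales CARS, ATEC (to assess the dynamics".

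The analysis paragraph appears twice in the same words, in Research methods and at the end of STATISTICAL CONSIDERATIONS. It says "Changes from the start of therapy and after 1, 2, 6, 12 months will be compared using the Wilcoxon criterion" and continues with "comparing data between the main group and the control group using non-parametric method, using the Mann-Whitney test". It gives no significance level, decisive visit, order of testing or adjustment. The visit list belongs to the Wilcoxon test; no visits are attached to the Mann-Whitney test.

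Therapy evaluation criteria has a third list: "Evaluation of the effect of treatment is carried out 1, 2, 3 and 6 months after treatment".

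On controls, OBJECT OF STUDY says "As a control group, 10 patients with a similar pathology will be examined", comparable in age, gender and degree of disorder according to a *paracopy* type. That word is not defined. No control visits or starting point are given.

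**The concern.** TASKS makes efficacy an aim: "To analyze the efficacy and safety of transfusion of hematopoietic cord blood cells in patients with autistic type disorder using rating scales". The list of data to be obtained includes how effective and appropriate the method is. A plan that must support such a statement needs to say which result decides it.

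Two things are at stake. First, with two scales and several visits all eligible, the chance that at least one comparison is significant by luck exceeds that of one fixed test, and a reader could not tell a prespecified result from a selected one. Second, the visit changes the question. Three injections are planned a month apart, so months 1 and 2 from the first infusion fall at about the second and third injections, before or just as the course is completed. Month 6 or 12 describes the completed course.

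**Working it through.** **Visit lists side by side**

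| Place | Months | Counted from |
|---|---|---|
| Research methods; end of STATISTICAL CONSIDERATIONS | 1, 2, 6, 12 | start of therapy |
| Therapy evaluation criteria | 1, 2, 3, 6 | after treatment |
| STATISTICAL CONSIDERATIONS, primary outcomes | 1, 2, 3, 6, 12 | initial infusion |

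Only months 1, 2 and 6 are in all three lists. The first and third starting points are plausibly the same. The second may differ: with injections at months 0, 1 and 2, visits 1, 2, 3 and 6 months after the last one are 2+1, 2+2, 2+3 and 2+6 = months 3, 4, 5 and 8 from the first. Controls have no infusion to count from.

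**Inputs.** From the documents: 10 per group, Mann-Whitney between groups, two scales, and the visit lists. The plan states no alpha or error rate, so there is no figure to reproduce. Assumed: two-sided 5% tests, no true effect, comparable and independent arms, complete untied data, Mann-Whitney at each of the four visits in the analysis paragraph, and equal correlation between visits and between scales over a range.

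**One fixed test, 10 v 10.** Under the null, U has mean 10×10/2 = 50 and variance 10×10×21/12 = 175, so SD 13.23. The exact test rejects at U ≤ 23 or U ≥ 77, with true size 4.3% (2.2% in favour of treatment). The normal approximation without continuity correction rejects at U ≤ 24, since (24−50)/13.23 = −1.965, with size 5.2% (2.6%).

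**Ceiling if all tests were independent at 5%.** 1 − 0.95⁴ = 18.5% for four tests; 1 − 0.95⁸ = 33.7% for eight.

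**With correlation** (simulation, 100,000 runs per setting, four visits). Each cell is exact / approximate test.

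| Scales | Correlation (time, scale) | Any false difference | Favouring treatment |
|---|---|---|---|
| 1 | 0.9 | 8.8% / 10.6% | 4.4% / 5.2% |
| 1 | 0.7 | 12.1% / 14.3% | 6.1% / 7.2% |
| 1 | 0.3 | 15.4% / 18.4% | 7.6% / 9.1% |
| 2 | 0.9, 0.7 | 14.7% / 17.3% | 7.4% / 8.7% |
| 2 | 0.7, 0.5 | 21.4% / 25.1% | 10.8% / 12.7% |
| 2 | 0.3, 0.3 | 28.0% / 32.9% | 14.3% / 16.9% |

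**Other visit counts**, either direction. With only the three visits common to all lists: one scale 8-12% exact and 9-14% approximate; two scales 13-22% and 16-26%. With all five visits: one scale 10-19% and 12-22%; two scales 16-33% and 19-39%.

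**If controls are pair-matched.** Suppose changes correlate within pairs while the unpaired exact test is used (four visits, either direction). At a within-pair correlation of 0.3, a single test has size about 2%, one scale about 4-7% and two scales about 8-15%. At 0.5 the figures are just under 1%, about 2-4% and about 4-7%. The unpaired test becomes conservative, but several looks still give about twice the single-test rate or more.

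**The case against.** The strongest objection is the matching. If *paracopy* means individual pairs, the independent-arms rates are too high and an unpaired test may be the wrong one. This stands: independence is an assumption, the rates fall as shown, and the fix must settle the question. It does not remove the defect, because the relative inflation persists.

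Second, no passage says that Mann-Whitney is run at every visit, and an assessment schedule is not a set of decisive tests. A reader might infer that the plan directs eight separate tests, or directs picking the best one. The documents do not support that: they are silent, and the percentages show what the silence permits.

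Third, a reader might take 15-33% as the chance of a false claim of benefit. It covers differences in either direction; only about half favour treatment, hence 7-17%.

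Fourth, a reader might think that CGI and ABC are also candidate outcomes, because Therapy evaluation criteria points back to the scales of the protocol's introduction and the background says "during the research studies the CARS, CGI and ABC scales were used". That sentence describes earlier research. Neither scale is in any planned method, and Stage 1 of the treatment protocol uses CARS and ATEC. The cross-reference needs tidying, but this is minor.

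Fifth, this is a small non-randomized study that reports medians and quartiles, and confounding may matter more. That is fair, but the plan does not call itself exploratory and it promises conclusions on effectiveness. If only description is meant, it should say so.

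**Conclusion.** The concern holds. The primary outcomes are unnamed, CARS and ATEC are unranked, there is no decisive visit, alpha or multiplicity rule, the visit lists conflict, and controls have no clock or schedule. These points rest on the text alone.

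The size is conditional. With two-sided 5% Mann-Whitney tests at four visits, comparable and independent arms of 10, and (time, scale) correlations from (0.9, 0.7) to (0.3, 0.3), a false difference favouring treatment is about 4-9% likely with one scale and 7-17% with two, against 2.2-2.6% for one fixed test. In either direction it is about 9-18% and 15-33%, against 4.3-5.2%. Pair matching with correlated changes would lower these figures, possibly to within 5% for one scale, so the absolute rates should not be quoted without the independence assumption. All figures assume comparable groups, which non-randomized allocation does not guarantee.

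**What to change.** Before data are seen, in STATISTICAL CONSIDERATIONS:

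- Name one primary scale. CARS or ATEC would serve equally for error control; ATEC is the only scale named in that section, as a baseline characteristic.
- Name one visit that is in all three lists, for example month 6, counted from the first infusion in the main group and from the baseline assessment in controls.
- Fix one test and a two-sided alpha of 0.05. State whether *paracopy* means individual pairs. If it does, use a Wilcoxon signed-rank test on within-pair differences in change; if not, use an exact Mann-Whitney test on change.
- Make all other scales, visits and within-group tests descriptive. If further claims are wanted, list a fixed family in advance and test it by Holm only after the primary is significant. The gate matters: a primary test at 0.05 plus ungated Holm on the rest gives about 5-9% overall.
- Reconcile the visit lists and starting points across Research methods, Therapy evaluation criteria and STATISTICAL CONSIDERATIONS. Say which scales the cross-reference to the introduction means, and state that controls are assessed at the primary visit.

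For the main group the cost is wording. For controls, up to one visit for each of 10 children may need to be confirmed or added. The downside is that another scale or visit can no longer carry the conclusion alone. The change controls multiplicity only; it does not remove bias from non-randomized allocation.

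### Safety follow-up is dated only from the third infusion, so no safety window applies to the 10 uninfused controls and no background event rate is assured

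*Combined protocol and SAP*

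**What the plan says.** All references are to the combined protocol and SAP.

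- **Groups.** OBJECT OF STUDY describes the infused group ("The protocol for testing the method will be carried out on 10 patients with autism spectrum disorder by transfusion of hematopoietic cord blood cells") and the comparison group ("As a control group, 10 patients with a similar pathology will be examined"). The controls stay on standard therapy and are chosen to resemble the infused children in age, sex and severity. The design is given as "Type of study: interventional, prospective, non-randomized with a control group".
- **Safety objective.** TASKS, item 3, is "To analyze the efficacy and safety of transfusion of hematopoietic cord blood cells in patients with autistic type disorder using rating scales". Safety also appears under CLINICAL PURPOSES and among the data to be obtained, and Expected results assumes that the transfusions will prove safe.
- **Safety follow-up.** Study Duration contains the only rule: "Research participants will be followed for safety for 12 months after the third study infusion".
- **Participation.** STATISTICAL CONSIDERATIONS says "Duration of study participation will be 12 months from the time of baseline infusion".
- **Infusions.** Treatment protocol, Stage 3: "Three-fold injection is planned at an interval of 1 month".
- **Analysis.** The two groups are compared by the Mann-Whitney test. No adverse-event definition, collection method, grading, causality assessment or analysis is given for either group.

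**The concern.** A follow-up window that opens or closes relative to an infusion cannot be placed on the calendar of a child who never has one. A site following the text would have no date from which to ask about events in a control, no visit at which to ask, and no date at which to stop.

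Children aged 3 to 15 will have illnesses and behavioural changes over a year whatever their treatment. If events are recorded only in the infused children, there is nothing from the same period and setting to set beside them. Later events, which fill most of the window, would be attributed or dismissed on opinion alone. The trial already has a concurrent group that could supply this context. Events not recorded prospectively in controls would have to be recovered by recall, which is a poor substitute.

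**Working it through.** The plan gives no event rate, significance level, power or safety precision, so there is no figure of its own to reproduce. The check sets the timings side by side and then asks what control data could show.

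**1. What each timed assessment is dated from**

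| Section | Assessment | Dated from |
|---|---|---|
| Study Duration | Safety, 12 months | Third infusion |
| STATISTICAL CONSIDERATIONS, opening text | Primary outcomes, months 1, 2, 3, 6, 12 | First infusion |
| Same | Participation, 12 months | First infusion |
| Therapy evaluation criteria | Effect, months 1, 2, 3, 6 | Treatment |
| Same | Immune status, 6 months | Last injection |
| Same | Cytokines, months 1, 2, 3 | First injection |
| Research methods; repeated at the end of STATISTICAL CONSIDERATIONS | Changes, months 1, 2, 6, 12 | Start of therapy |

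Only the last origin could conceivably exist for a control. For a child on background standard therapy, the plan does not say what date it is.

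**2. Who counts as a participant**

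Accrual says "approximately 4 weeks of accrual will be necessary to enroll 10 participants", at 2 to 3 a week. The midpoint gives 10 / 2.5 = 4 weeks; all 20 children would take 20 / 2.5 = 8 weeks. In that paragraph the term matches the infused group alone. The Demographics paragraph, however, summarizes all research participants, which would be an odd place to leave the controls out. The term is not used consistently enough to settle the matter.

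**3. Calendar of the infused children**

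Infusions fall at months 0, 1 and 2. Safety follow-up ends at 0 + 1 + 1 + 12 = month 14. Participation ends at month 12. The two statements differ by about 2 months.

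**4. What infused children alone can show**

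With 0 events in 10, the exact 95% upper limit is 1 − 0.05^(1/10) = 25.9% one-sided, or 1 − 0.025^(1/10) = 30.8% two-sided. If the background risk of an event is p, the chance that at least one of 10 has one with no treatment effect is 1 − (1 − p)^10. The risks below are assumptions:

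- p = 2%: 18.3%
- p = 5%: 40.1%
- p = 10%: 65.1%
- p = 30%: 97.2%

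These figures show why context is useful. They do not measure the gap, because they are the same whether or not controls are followed.

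**5. What 10 controls would add** (Fisher's exact test, two-sided 5% level assumed)

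- Smallest significant contrast with no control events: 5/10 against 0/10 (p = 0.033); 4/10 against 0/10 gives p = 0.087.
- With 1, 2 or 3 controls affected, at least 7, 8 or 9 infused children must be affected.
- Power for a 20-point excess: 5.5% to 5.7% over assumed background risks of 10% to 70%.
- Power for a 30-point excess: 12.3% to 15.2% over background risks of 10% to 50%.
- Children per group for 80% power at a 20-point excess (normal approximation): 62 to 93.
- Chance that 10 fully followed controls show no event, (1 − p)^10: 82% at p = 2%, 60% at 5%, 35% at 10%.

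**The case against.** The strongest reply is that nothing excludes the controls. The rule speaks of research participants generally, and its wording may be careless rather than deliberate. This stands. A reader might infer that controls have no safety follow-up by design; the documents support only that theirs is undefined.

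A reader might also infer that monitoring begins only at the third infusion. The sentence fixes how long follow-up lasts, not when it begins, and Stage 3 requires a biological compatibility test at the start of injection. It remains true that no event collection is described between the first and third infusions.

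A third tempting reading is that, without control data, events in infused children cannot be told apart from ordinary childhood events. That is too absolute. Reactions during or soon after an infusion can be judged partly by timing. For later events, 10 non-randomized controls would not give a reliable separation either, as step 5 shows, and for rare events the control group would often show none.

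It is also fair to say that the wider gap is the absence of any adverse-event collection plan in either group, and that the missing index date affects the controls' efficacy visits too. Both points widen the problem rather than answer it. The control window still has to be written, because general adverse-event wording dated from infusion would again miss these 10 children.

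**Conclusion.** The point holds in limited form. As written, 10 of the 20 children have no index date, safety window or safety visit, and adverse-event collection is unspecified for the other 10. The plan therefore assures no background event rate for an objective that it states several times. This rests on the text alone and needs no assumed rate.

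What correction would gain is modest: a descriptive background count from the same period, not a test of harm. The power figures assume a two-sided 5% level and the stated ranges of background risk, none of which comes from the documents. Separately, the month-14 and month-12 end dates conflict and must be reconciled. The change is worth making before enrolment because it decides what is recorded.

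**What to change.** Reword Study Duration and add a short safety paragraph under STATISTICAL CONSIDERATIONS:

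1. Give every control an index date. If children are individually paired, use the first-infusion date of the corresponding infused child. If not, use the control's own baseline assessment. The plan should say which applies, since it describes no pairing procedure and its between-group test treats the groups as independent.
2. Define what counts as an adverse event and a serious one. Collect events in both groups from the index date (the first infusion for infused children), with the same questions, at the same visits and over the same length of follow-up.
3. Tabulate by group the number of children with any event and with a serious event, with exact confidence intervals.
4. State that the comparison is descriptive: 10 against 10, non-randomized, very low power. Absence of a difference is not evidence of safety.
5. Reconcile the safety window after the third infusion with the duration of participation, and apply the result to both groups.

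The cost is protocol wording and a few minutes of questions per visit. Control visits must also be scheduled explicitly to match the infused group's scale visits, since the plan gives them no timetable. No extra children are needed.
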